### **9.5. Average Daily Dose**

Average daily dose (mg/day) is defined as the cumulative dose of study drug divided by the dose exposure.

### **9.6. Relative Dose Intensity**

Relative dose intensity will be calculated as the dose intensity divided by the protocol daily dose x 100. The protocol daily dose is defined as  $300*14/21$  mg/day for subjects who received CC-486 at a starting dose of 300 mg daily. For the first 6 Asian-Pacific Island ethnicity subjects evaluable for safety who received CC-486 at a starting dose of 200 mg, the protocol daily dose is defined as  $200*14/21$  mg/day.

Descriptive statistics for the cumulative dose (mg), dose intensity (mg/day), relative dose intensity, as well as a frequency summary of subjects within each relative dose intensity categories ( $\geq 90\%$ ,  $< 90\%$  to  $80\%$ ,  $< 80\%$  to  $70\%$ , and  $< 70\%$ ) will be provided.

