**Treatment:** Subjects meeting eligibility criteria must start treatment within 21 days of signing the informed consent form (ICF). For all subsequent visits, an administrative window of  $\pm$  2 days is permitted. Treatment cycles are 21 days in duration. All evaluations should be performed prior to dosing on the visit day, unless otherwise specified. CC-486 will be administered at a dose of 300 mg orally (PO) daily (QD) on Days 1 to 14 of a 21-day cycle. However, the first 6 subjects of Asian-Pacific Island ethnicity evaluable for safety will receive CC-486 at a dose of 200 mg orally QD on Days 1 to 14 of 21 days of Cycle 1; and if well-tolerated, and there are no safety concerns, subsequent subjects of Asian-Pacific Island ethnicity will be treated at the 300 mg QD on Days 1 to 14 of a 21-day cycle.

**Response Assessment by Response Evaluation Criteria In Solid Tumors (RECIST) v 1.1:** Response assessments (tumor evaluations) should be performed at screening within 28 days before the start of investigational product (IP), and every 6 weeks ( $\pm$  5 days) from Cycle 1 Day 1 (C1D1) for the first 3 tumor evaluations and then every 9 weeks until disease progression, start of a new anticancer therapy, or withdrawal of consent from the entire study. Evaluation of response will be performed using RECIST v1.1.

An independent radiological assessment of responses will be conducted using RECIST v1.1.

Response assessments include computed tomography (CT) scan or magnetic resonance imaging (MRI) of the head and neck with supraclavicular node imaging, the chest and abdomen/pelvis,

neurological examination with facial nerve evaluation, and bone scans at baseline for all subjects. Bone scans will be repeated only if the subject is symptomatic or with known bone metastasis. The same mode of imaging for lesion evaluation at screening must be used consistently throughout the study.

All subjects with evidence of objective tumor response (CR or PR) should have the response confirmed with repeat assessments at the next scheduled scan, but after no less than 4 weeks. Response assessments must have occurred  $\geq$  6 weeks from Cycle 1 Day 1 to be considered as SD for a best response.

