## **9. STUDY TREATMENTS AND EXTENT OF EXPOSURE**

Study treatment and extent of exposure summaries will be provided based on the safety population. Treatment duration, dose exposure, number of cycles, number of doses, cumulative dose, dose intensity, average daily dose, relative dose intensity, dose reduction, and dose interruption, number of subjects dosed at each cycle and maximum number of cycles received per subject will be summarized. Individual subject listings of exposure to study drug will be provided. Column headers will be displayed as follows: 'AP 200 mg', '300 mg', and 'Total'.

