### **9.1. Treatment Duration**

The treatment start date is the date of the first dose of study drug and the treatment end date is the date of the last non-missing dose of study drug.

Treatment duration (in days) is calculated as (the treatment end date – the treatment start date + 1). Summary statistics for treatment duration (in days) will be provided. Descriptive statistics will be provided for the total number of treatment cycles subjects received and for the number of doses received.

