### **9.2. Dose Exposure**

Dose exposure (days) for overall is defined as the total number of actual days on CC-486 (dose > 0 mg) during treatment phase.

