### **9.4. Dose Intensity**

Dose intensity reported in mg/day will be calculated as the cumulative dose divided by the treatment duration in days which is defined in Section 9.1 above.

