## 9.7. Dose Reduction, Interruption and Overdose

Dose reduction is defined as a non-zero dose administered after the Cycle 1 Day 1 (C1D1) dose which is at a lower dose level than the dose the subject received at the previous dosing day.

Dose interruption occurs if the record of actual administered dose is zero except as required by the protocol. Consecutive zeros are counted as one interruption.

Overdose, as defined for this protocol, refers to the treatment CC-486 only. On a per dose basis, an overdose is defined as any amount over the protocol-specified dose of CC-486 assigned to a given subject, regardless of any associated AEs or sequelae.

On a schedule or frequency basis, an overdose is defined as anything more frequent than the protocol required schedule or frequency.

Dose reduction, interruption and overdose will be summarized as follows:

- Number and percentage of subjects with at least one dose reduction, reasons for each reduction, and frequency of reductions
- Summary statistics (sample size, mean, median, STDEV, first and third quartiles, minimum, and maximum) for time to first reduction
- Number and percentage of subjects with at least 1 dose interruption, reasons for each interruption and frequency of interruption
- Number and percentage of subjects who had  $> 5$  days of dose interruption due to AE, and had  $\geq 14$  days of dose interruption due to AE
- Summary statistics (sample size, mean, median, STDEV, first and third quartiles, minimum, and maximum) for time to first interruption and total days of interruption

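### Relative dose intensity mixes two time bases: if treatment ends at the last dose taken, full on-time dosing scores above 100%, and as much as 150%

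*SAP*

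**What the plan says.** The measure is built from three definitions in the SAP.

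- Section 9.1: treatment starts at the first dose, and "the treatment end date is the date of the last non-missing dose of study drug". Duration is end date minus start date plus 1.
- Section 9.4: dose intensity is "calculated as the cumulative dose divided by the treatment duration in days which is defined in Section 9.1 above".
- Section 9.6: "Relative dose intensity will be calculated as the dose intensity divided by the protocol daily dose x 100". The protocol daily dose is 300*14/21 mg/day for a 300 mg start and 200*14/21 mg/day for the first six evaluable Asian-Pacific Island subjects, who start at 200 mg.

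Section 4.1 sets the schedule: dosing on Days 1 to 14, and "Treatment cycles are 21 days in duration".

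Section 9.6 then plans "Descriptive statistics for the cumulative dose (mg), dose intensity (mg/day), relative dose intensity", together with a count of subjects in four bands: 90% or more, below 90% to 80%, below 80% to 70%, and below 70%.

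Two other definitions bear on the reading. Section 9.2 defines dose exposure as "the total number of actual days on CC-486 (dose > 0 mg) during treatment phase", so it restricts to positive doses where Section 9.1 does not. Section 9.7 says "Dose interruption occurs if the record of actual administered dose is zero except as required by the protocol", so it allows for zero records that the protocol requires.

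**The concern.** The clock for dose intensity stops at the last dose and leaves out the rest days that follow it. The reference dose is spread over 21 days and includes them. The two averages are not comparable, and the ratio is too high.

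A score above 100% for a fully adherent subject looks odd but leaves that subject in the correct band. The harm falls on subjects who missed doses: the same inflation can lift them into the top band, so that the table overstates how much of the planned dose was given.

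The effect is largest for short treatment, which the SAP expects. Exposure is summarised in the Safety Population, which is anyone with one dose. Section 4.1 plans to replace subjects who progress before the end of Cycle 1, and once dosed they stay in this table. The first tumour assessment is at 6 weeks, the end of Cycle 2.

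**Working it through.** **Inputs.** Dosing on 14 of 21 days (Section 4.1); duration from first to last dose (9.1); dose intensity as cumulative dose over that duration (9.4); protocol daily dose (9.6). The last dose is read as the last dose taken.

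**The plan's own figure.** 300 × 14/21 = 200 mg/day; 200 × 14/21 = 133.3 mg/day. Both reproduce, as averages over a full 21-day cycle.

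**Full on-time dosing, k complete dosing periods, 300 mg.** Cumulative dose = 300 × 14 × k = 4,200k mg. Duration = 21(k − 1) + 14 = 21k − 7 days. Relative dose intensity = 4,200k/(21k − 7)/200 = 3k/(3k − 1).

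| k | Dose (mg) | Days | mg/day | Relative dose intensity |
|---|---|---|---|---|
| 1 | 4,200 | 14 | 300.0 | 150.0% |
| 2 | 8,400 | 35 | 240.0 | 120.0% |
| 3 | 12,600 | 56 | 225.0 | 112.5% |
| 4 | 16,800 | 77 | 218.2 | 109.1% |
| 6 | 25,200 | 119 | 211.8 | 105.9% |

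For k = 1 the dose intensity of 300 mg/day equals the average daily dose of Section 9.5 (4,200 mg over 14 dosing days). The ratio is then a dosing-day average over a whole-cycle average.

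**Stops within a dosing period, no missed dose.** For a last dose on Day d of Cycle k, the score is 1.5 × [14(k − 1) + d]/[21(k − 1) + d].

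- Cycle 1, any d from 1 to 14: 150%.
- Cycle 2: 102.3% (Day 1: 4,500/22/200) to 120% (Day 14).
- Cycle 3: 101.2% to 112.5%.
- Cycle 12: 100.2% to 102.9%.

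The peak therefore needs no completed dosing period, and the score stays above 100% throughout.

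**Delays.** Four full cycles with 0, 7 or 14 days of total delay score 16,800/77/200 = 109.1%, 16,800/84/200 = 100% and 16,800/91/200 = 92.3%.

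**Effect on the top band** (last planned dose taken, no delay).

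- 9 of 14 doses, 64.3% of plan: 2,700/14/200 = 96.4%. Over the whole cycle: 2,700/21/200 = 64.3%, the lowest band.
- 21 of 28 doses, 75% of plan: 6,300/35/200 = 90.0%. Over whole cycles: 6,300/42/200 = 75.0%, the third band.

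In general the share of plan that scores 90% is 90 × (3k − 1)/(3k): 60%, 75%, 80% and 82.5% for k = 1 to 4.

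**200 mg start.** Cycle 1: 2,800/14/133.3 = 150%. The factor 3k/(3k − 1) holds in later cycles only if the dose stays at 200 mg. Section 4.1 gives 200 mg for Cycle 1, and the SAP does not state what these subjects receive afterwards.

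**The other reading.** If zero records on rest days count as non-missing doses, the end date moves to Day 21 of the last cycle, and full dosing scores 4,200k/(21k)/200 = 100%.

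**The case against.** The strongest objection is to the reading. A recorded zero is non-missing; Section 9.2 restricts to positive doses where Section 9.1 does not; and Section 9.7 shows that protocol-required zeros are foreseen. On that view the text may already give 100%, and the fault is only an undefined end date. This stands as a possibility. It does not clear the text, because the SAP nowhere says that rest-day zeros count and a rest day is not naturally called a dose. Two programmers could report 150% and 100% for the same subject.

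The second objection is low consequence, and it stands. Section 9 also tabulates "number of cycles, number of doses, cumulative dose, dose intensity, average daily dose, relative dose intensity, dose reduction, and dose interruption", with subject listings, so missed doses remain visible. Summary statistics include the maximum, so a value of 150% would show there, though not in the band table.

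The third is that a whole-cycle base errs the other way for subjects who stop mid-cycle. This also stands. With no missed dose, a stop on Day 1 of Cycle 2 would score 4,500/42/200 = 53.6%, and on Day 1 of Cycle 5 17,100/105/200 = 81.4%, against 102.3% and 100.6% under the SAP. A second figure is therefore a necessary part of the fix.

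A reader might infer that many subjects will be placed in the wrong band. The SAP gives no distribution of cycles or adherence, so that number cannot be stated. A reader might also infer that the efficacy conclusion is affected. Relative dose intensity enters no test, stopping rule or population definition.

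**Conclusion.** Wrong as written, with low consequence. On the natural reading of Section 9.1, relative dose intensity exceeds 100% for every subject who takes the full dose on time: by 50 percentage points for any stop in the first dosing period, by 20 after two full periods and by 9.1 after four. Subjects with 64% or 75% of planned dose over one or two cycles can reach the top band.

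The size rests on three assumptions: the last dose is the last dose taken, there are no delays between cycles and, in the band examples, the last planned dose was taken. For the 200 mg group beyond Cycle 1 it also assumes a constant 200 mg dose.

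**What to change.** 1. In Section 9.1, state that the last dose means the last dose above 0 mg.
2. In Section 9.6, compute the dose intensity used for relative dose intensity over the days from first dose to the later of Day 1 of the last cycle + 20 and the last dose date. Footnote that this base differs from Section 9.4: four full cycles give 218.2 mg/day there and 16,800/84 = 200.0 mg/day here.
3. For subjects who permanently stop before completing the last cycle's dosing days, always also show the percentage of scheduled dose received up to the last dose. For a stop on Day 1 of Cycle 2 with no missed dose this is 15/15 = 100%, beside 53.6%.

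Under item 2, full on-time dosing scores exactly 100%, and delays still lower the score: four full cycles with 7 or 14 days of delay give 92.3% and 85.7%. Taking the later of the two dates matters when dosing within a cycle is stretched. Fourteen doses in Cycle 1 with the last on Day 24 score 4,200/24/200 = 87.5%; ending at Day 21 would give 100%.

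The last-cycle rule in Section 5.1 does not serve here, because it stops at the discontinuation date when that comes first. It can stay as it is for cycle assignment.

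Cost: a few sentences, slightly more programming, lower reported values and one extra figure for mid-cycle stoppers.

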## 9.7. Dose Reduction, Interruption and Overdose

Dose reduction is defined as a non-zero dose administered after the Cycle 1 Day 1 (C1D1) dose which is at a lower dose level than the dose the subject received at the previous dosing day.

Dose interruption occurs if the record of actual administered dose is zero except as required by the protocol. Consecutive zeros are counted as one interruption.

Overdose, as defined for this protocol, refers to the treatment CC-486 only. On a per dose basis, an overdose is defined as any amount over the protocol-specified dose of CC-486 assigned to a given subject, regardless of any associated AEs or sequelae.

On a schedule or frequency basis, an overdose is defined as anything more frequent than the protocol required schedule or frequency.

Dose reduction, interruption and overdose will be summarized as follows:

- Number and percentage of subjects with at least one dose reduction, reasons for each reduction, and frequency of reductions
- Summary statistics (sample size, mean, median, STDEV, first and third quartiles, minimum, and maximum) for time to first reduction
- Number and percentage of subjects with at least 1 dose interruption, reasons for each interruption and frequency of interruption
- Number and percentage of subjects who had  $> 5$  days of dose interruption due to AE, and had  $\geq 14$  days of dose interruption due to AE
- Summary statistics (sample size, mean, median, STDEV, first and third quartiles, minimum, and maximum) for time to first interruption and total days of interruption

## 10. EFFICACY ANALYSIS

All efficacy results will be summarized for the efficacy evaluable population. If Stage 2 is conducted, analyses will be performed for PFS and OS in addition to ORR. Column headers will be displayed as follows: 'AP 200 mg', '300 mg', and 'Total'.

### 10.1. Multiplicity

There is no multiplicity adjustment for the efficacy endpoints.

### 10.2. Analysis of the Efficacy Endpoints

The primary efficacy endpoints are ORR and PFS.

Overall response rate is defined as the combined incidence of CR and PR, confirmed no less than 4 weeks after the criteria for response are first met, based on independent radiology assessment using RECIST version 1.1. After the enrollment of 51 patients, if more than 14 responders are observed, the null hypothesis ( $ORR \leq 20\%$ ) will be rejected, the true ORR will be concluded to be  $> 20\%$ . The point estimate and two-sided 90% CI of ORR will be provided using the Clopper-Pearson method (Clopper, 1934).

Progression-free survival will be based on independent radiology assessed response using RECIST v1.1. Progression-free survival is defined as the time from the date of start of the study treatment to the date of disease progression or death (any cause) on or prior to the data cut-off date for the statistical analysis, whichever occurs earlier. Subjects who do not have disease progression or have not died as of the data cut-off date will be censored at the time of the last radiologic assessment prior to the data cut-off date. In the event that a new anticancer therapy is initiated for a subject prior to documented progression, the subject will be censored at the time of the last radiologic assessment where the subject was documented to be progression-free prior to the initiation of the new anticancer therapy. Subjects with a single missing radiologic assessment prior to a visit with documented disease progression (or death) will be analyzed as a PFS event at the time of the radiologic assessment that shows progression (or death). Subjects with  $\geq 2$  consecutive missing radiologic assessments prior to a visit with documented disease progression (or death) will be censored at the time of the last radiologic assessment where the subject was documented to be progression-free prior to the first of the  $\geq 2$  consecutive missing visits.

The Kaplan-Meier (K-M) method will be used to estimate PFS distribution, and the medians with two-sided 90% CIs will be reported. Since the study did not enter the second stage, no hypothesis testing will be conducted for PFS. The K-M estimates of PFS rates at each 2-month interval will be provided. Kaplan-Meier curves for PFS will be presented.

Disease control rate, a secondary efficacy endpoint, is defined as CR and PR, confirmed  $\geq 4$  weeks after the criteria for response are first met, and SD  $\geq 16$  weeks from the first treatment, based on independent radiology assessment using RECIST v1.1. The point estimate and two-sided 90% CI of DCR will be provided using the Clopper-Pearson method (Clopper, 1934).

Overall survival, another secondary efficacy endpoint, is defined as the time from first treatment to death of any cause. Subjects who did not die by the end of study or the clinical data cut-off date will be censored on the last-known-to-be-alive date or the clinical cut-off date, whichever is earlier.

The survival distribution of OS will be estimated using K-M method. The median including two-sided 90% CI will be provided. The survival rates will be provided at each 2-month interval. Kaplan-Meier curves for OS will also be presented.

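### SAP 10.2: the general PFS censoring rule omits the documented-progression-free condition that its two companion rules carry (minor; any effect on the K-M curve is upward)

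*SAP*

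**What the plan says.** All three PFS censoring rules stand in one paragraph of SAP Section 10.2.

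- **General rule.** It applies to "Subjects who do not have disease progression or have not died as of the data cut-off date". They "will be censored at the time of the last radiologic assessment prior to the data cut-off date". Nothing is required of the result of that assessment.
- **New anticancer therapy.** Here "the subject will be censored at the time of the last radiologic assessment where the subject was documented to be progression-free", before the new therapy began.
- **Two or more consecutive missing assessments before progression or death.** The subject is "censored at the time of the last radiologic assessment where the subject was documented to be progression-free prior to the first of the" missing visits.

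The time origin is first dose: "Progression-free survival is defined as the time from the date of start of the study treatment". The event is progression on independent radiology review, or death, whichever comes first. Section 4.1 places scans every 6 weeks for the first three evaluations and every 9 weeks after that, with a screening scan up to 28 days before dosing. Section 10 analyses efficacy in the Efficacy Evaluable Population (Section 5.2.3). Section 10.2 states that PFS will not be tested, because the study did not enter Stage 2. It is reported as a K-M median with 90% CI, 2-monthly rates and curves.

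**The concern.** One primary endpoint has two different censoring anchors. The special rules stop the clock at the last point where the subject was known to be progression-free. The general rule stops it at the last scan of any kind. No section of the SAP says how a scan that independent review cannot evaluate is to be handled, so the literal text lets such a scan extend progression-free time.

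The affected subjects need not be a random subset. Route 1 of the Efficacy Evaluable Population admits a subject who had at least 2 cycles and stopped for progressive disease, without saying by whose assessment. The post-discontinuation tumour follow-up in Section 4.1 is for those who stop for other reasons. A subject stopped for investigator-assessed progression, with a last scan that independent review could not read, may therefore have no later scan. If no new therapy follows, the general rule censors that subject as event-free at the unreadable scan.

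The conjunction is a second fault. A subject who has progressed but is alive satisfies one half of the *or* condition, so the literal sentence censors someone who already has a PFS event.

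At stake are the reported K-M median, its interval and the 2-monthly rates. No test or stage decision is affected.

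**Working it through.** The SAP states no figure on this point to reproduce. The check is therefore the direction of the effect first, then its size under stated assumptions.

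**1. Same scans, two dates.** Take two event-free subjects with readable scans at weeks 6 and 12 and an unreadable last scan at week 18. The one who then starts new therapy is censored at week 12. The one who does not is censored at week 18. The gap is 6 weeks here and 9 weeks later in the schedule.

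**2. Direction.** The K-M estimate is the product of (1 − d/r) over event times, with d events among r at risk. Moving a censoring time later leaves every d unchanged and can only increase r. Each factor therefore stays the same or rises, and the written rule can never give a lower curve than the corrected one. With 1 event and 8 at risk, the factor is 7/8 = 87.5%. If one of the eight should already have been censored, it is 6/7 = 85.7%.

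**3. Size, moderate assumptions.** Inputs not in the SAP: exponential PFS, median time to loss from imaging 18 months, cut-off 9 to 18 months after start, and a stated share of unreadable last scans. K-M PFS at 6 months, 20,000 simulated subjects per row:

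| True median | Unreadable last scans | Written rule | Corrected rule | Difference (points) |
|---|---|---|---|---|
| 5 months | 5% | 56.5% | 56.4% | +0.1 |
| 5 months | 10% | 56.7% | 56.5% | +0.2 |
| 5 months | 20% | 56.0% | 55.6% | +0.4 |
| 8 months | 20% | 70.1% | 69.8% | +0.3 |

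The K-M median was the same under both rules in every row. In 3,000 trials of n = 17 with a 5-month median and 10% unreadable, the mean difference was +0.2 points, the largest +6.3 and none negative. The median changed in 1.9% of trials.

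**4. Size, harsher assumptions.** Suppose that at each scan a fraction q of subjects have an unreadable scan and are then lost. With a 5-month median (5 × 30.44 = 152.2 days), the progression probability per 42-day interval is h = 1 − 2^(−42/152.2) = 0.174. The true week-18 PFS is (1 − 0.174)³ = 56.3%. Under the written rule the lost subjects stay in the risk set without being able to contribute an event, so h becomes h(1 − q) at the affected scans.

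A subject lost after an unreadable week-6 scan meets neither route in Section 5.2.3, so the first scan is left unaffected: S = (1 − h) × [1 − h(1 − q)]².

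- q = 3%: 0.8259 × 0.8311² = 57.1%, +0.7 points
- q = 5%: 0.8259 × 0.8346² = 57.5%, +1.2 points
- q = 10%: 0.8259 × 0.8433² = 58.7%, +2.4 points

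Simulated trials of 17 give about 0.7, 1.2 and 2.5, the same within simulation error. In them about 9, 14 and 26% of all subjects end on an unreadable scan. The week-18 value is also the 6-month value, since the next scan (week 27) falls after 6 months, so steps 3 and 4 describe the same point on the curve.

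**5. Yardstick.** The sampling SD of the K-M estimate at that time with n = 17 is about 12 points.

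**6. Subject with only a screening scan.** That scan precedes first dose by up to 28 days, so the general rule gives a time of zero or below. Route 2 requires at least two post-screening assessments. Only a route 1 subject could be in this position.

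**The case against.** The strongest reply is that a sensible programmer would not follow the sentence literally. PFS is tied to independently assessed RECIST response, so the last radiologic assessment can be taken as the last one that yielded a response, in line with the next two rules. The event definition precedes the censoring rule, so nobody would censor a living progressor. PFS is descriptive in a stopped single-arm study, and any shift is far below sampling noise.

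Much of this stands. It limits the point to a minor one. It does not remove it: the qualifying words appear twice in the paragraph and are absent once, which invites a reader to treat the difference as intended.

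A reader might also infer more than the document supports.

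- **That a screening scan is credited as progression-free time.** It is not. The scan lies before the time origin, and a zero or negative time does not move the curve.
- **That PFS is biased upward as a fact.** This needs censored subjects whose last scan is unreadable, and the SAP gives no such rate.
- **That the bias is near 4 points.** Per-scan loss of 10% with week-6 drop-outs retained gives (1 − 0.174 × 0.90)³ = 60.0%, or +3.6 points. But then about 33% of all subjects end on an unreadable scan, and the figure includes people whom Section 5.2.3 excludes.
- **That a lone bone scan sets the censoring date.** Section 4.1 says "Bone scans will be repeated only if the subject is symptomatic or with known bone metastasis", but no section makes a bone scan by itself a response assessment.

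**Conclusion.** The inconsistency is real and minor. The general censoring rule lacks a condition that both companion rules carry. If followed as written, it can only raise the PFS curve or leave it unchanged.

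The size rests on assumptions, because the SAP gives no rate of unreadable last scans. It is about 0.1 to 0.4 points on 6-month PFS if 5 to 20% of last scans are unreadable. It is about 0.7 to 2.5 points at week 18 under per-scan loss of 3 to 10% with week-6 drop-outs excluded. Both are small against an SD of about 12 points at n = 17, although a single subject can occasionally move one trial's estimate by several points.

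The *or* is a drafting error that contradicts the event definition. The screening-scan issue is confined to an undefined or negative time for a rare route 1 subject. No hypothesis test and no stage decision depends on any of this.

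**What to change.** Replace the general censoring sentence in SAP Section 10.2 with:

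> Subjects who have neither progressed nor died by the data cut-off will be censored at the last evaluable radiologic assessment, on or before the cut-off, at which independent review documented no progression. Subjects with no such post-baseline assessment will be censored at Day 1.

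This gives all three rules the same anchor, corrects the conjunction, and assigns time from first dose to subjects without an evaluable post-baseline assessment.

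The cost is one sentence and one programming condition that the two special rules already need. Reported PFS may be slightly less favourable. The change should be made before database lock, in keeping with the pre-specification aim in SAP Section 2.
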